10.0 Adverse Event (AE) Reporting and Monitoring

The site principal investigator is responsible for reporting any/all adverse events to the sponsor as described within the protocol. Refer to the adverse event and serious adverse event sections of the protocol for detailed information.

The sponsor/sponsor-investigator is responsible for notifying FDA and all participating investigators in a written safety report of any of the following:

- Any suspected adverse reaction that is both serious and unexpected.
- Any findings from laboratory animal or *in vitro* testing that suggest a significant risk for human subjects, including reports of mutagenicity, teratogenicity, or carcinogenicity.
- Any findings from epidemiological studies, pooled analysis of multiple studies, or clinical studies, whether or not conducted under an IND and whether or not conducted by the sponsor, that suggest a significant risk in humans exposed to the drug.
- Any clinically important increase in the rate of a serious suspected adverse reaction over the rate stated in the protocol or Investigator's Brochure (IB).

Definitions

Adverse Event

Any untoward medical occurrence associated with the use of a drug in humans, whether or not considered drug related.

Suspected Adverse Reaction

Any adverse event for which there is a reasonable possibility that the drug caused the adverse event.

Expedited Reporting

Events reported to sponsor within 24 hours, 5 days or 10 days of study team becoming aware of the event.

Routine Reporting

Events reported to sponsor via case report forms

Events of Interest

Events that would not typically be considered to meet the criteria for expedited reporting, but that for a specific protocol are being reported via expedited means in order to facilitate the review of safety data (may be requested by the FDA or the sponsor).

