10.31 EXPECTED Serious Adverse Events: Protocol Specific Exceptions to Expedited Reporting

For this protocol only, the following Adverse Events/Grades are expected to occur within this population and do not require Expedited Reporting. These events must still be reported via Routine Reporting (see Section 10.53).*

System Organ Class (SOC)	Adverse event/ Symptoms	CTCAE Grade at which the event will not be expeditedly reported.
General disorders and	Fatigue	≤Grade 3
administrations site conditions	Malaise	≤Grade 3
Blood and lymphatic	Febrile Neutropenia	≤Grade 3
system disorders	Neutrophil count decreased	≤Grade 3
	Thrombocytopenia	≤Grade 3
Investigations	Blood bilirubin increased	≤Grade 3
Metabolism and nutrition disorders	Tumor lysis syndrome	≤Grade 3

These exceptions only apply if the adverse event does not result in hospitalization. If the adverse event results in hospitalization, then the standard expedited adverse events reporting requirements must be followed.

The following hospitalizations are not considered to be SAEs because there is no "adverse event" (i.e., there is no untoward medical occurrence) associated with the hospitalization:

- Hospitalizations for respite care
- Hospitalization planned before informed consent (where the condition requiring the hospitalization has not changed post study drug administration)
- Hospitalization for administration of study drug or insertion of access for administration of study drug
- Hospitalization for routine maintenance of a device (e.g., battery replacement) that was in place before study entry
- *Report any clinically important increase in the **rate** of a serious suspected adverse reaction (at your study) site over that which is listed in the protocol or investigator brochure as an expedited event.
- *Report an expected event that is greater in severity or specificity than expected as an expedited event.
- *An investigational agent/intervention might exacerbate the expected AEs associated with a commercial agent. Therefore, if an expected AE (for the commercial agent) occurs with a higher degree of severity or specificity, expedited reporting is required.

A list of known/expected AEs is reported in the investigator brochure, package insert or the literature, including AEs resulting from a drug overdose

10.311 Death

- Any death occurring within 30 days of the last dose, regardless of attribution to an agent/intervention under an IND/IDE requires expedited reporting within 24-hours.

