infant, the investigator must obtain consent from the pregnant woman and the newborn infant's parent or legal guardian before any data collection can occur. A consent form will need to be submitted to the IRB for these subjects if a pregnancy occurs. If informed consent is not obtained, no information may be collected.

In cases of fetal death, miscarriage or abortion the mother is the patient. In cases where the child/fetus experiences a serious adverse event other than fetal death, the child/fetus is the patient.

NOTE: When submitting

the potential risk of

exposure of the fetus to the investigational agent(s) or chemotherapy agent(s) should be documented in the "Description of Event" section. Include any available medical documentation.

- **10.4** Expedited Adverse Event Reporting Requirements for IND/IDE Agents
 - 10.41 Phase 1 and Early Phase 2 Studies: Expedited Reporting via the **MedWatch form** for Adverse Events That Occur Within 30 Days¹ of the Last Dose of the Investigational Agent

FDA REPORTING REQUIREMENTS FOR SERIOUS ADVERSE EVENTS (21 CFR Part 312)

NOTE: Investigators MUST immediately report to the sponsor ANY Serious Adverse Events, whether or not they are considered related to the investigational agent(s)/intervention (21 CFR 312.64)

An adverse event is considered serious if it results in ANY of the following outcomes:

- 1) Death
- 2) A life-threatening adverse event
- 3) An adverse event that results in inpatient hospitalization or prolongation of existing hospitalization for ≥ 24 hours
- 4) A persistent or significant incapacity or substantial disruption of the ability to conduct normal life functions
- 5) A congenital anomaly/birth defect.
- 6) Important Medical Events (IME) that may not result in death, be life threatening, or require hospitalization may be considered serious when, based upon medical judgment, they may jeopardize the patient or subject and may require medical or surgical intervention to prevent one of the outcomes listed in this definition. (FDA, 21 CFR 312.32;ICH E2A and ICH E6).

ALL SERIOUS adverse events that meet the above criteria MUST be immediately reported to the sponsor within the timeframes detailed in the table below.

Hospitalization	Grade 1 and Grade 2 Timeframes	Grade 3-5 Timeframes
Resulting in Hospitalization ≥24 hrs	7 Calendar Days	24-Hour; 3 Calendar Days
Not resulting in Hospitalization ≥ 24 hrs	Not required	24-Hour, 3 Calendar Days

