Genentech Adverse Events of Special Interest (AESI): AEs of Special Interest are defined by Genentech as a potential safety problem identified as a result of ongoing safety monitoring of their products. As such, surveillance for the AESIs below MUST be undertaken at each treatment evaluation. The following events are events of special interest and will require expedited reporting AT ANY GRADE and will be treated like a serious adverse event with regard to reporting timeframes.

Events of clinical interest for this trial include:

Potential drug-induced liver injury (DILI) as defined by Hy's Law

- a. Investigations
 - i. Alanine aminotransferase increase
 - ii. Aspartate aminotransferase increase

- b. Metabolism and nutritional disorders
 - i. Tumor Lysis Syndrome
- c. Secondary Malignancies
 - i. Treatment related secondary malignancy

Adverse Event	Needed		ACCRU timeline to report to sponsor
Non-Serious Adverse Event (Sections 10.52- 10.53)	Adverse Events form (see CRF packet)	At each evaluation	Quarterly
Adverse Events of Special Interest (Section	Adverse Events of Special Interest Form**	At each occurrence	Within 1 business day of receipt
10.41 special instructions)	Adverse Events form (if criteria in 10.5 is met)		Quarterly
Pregnancy (Section 10.314)	MedWatch Form**	At each occurrence	Within 1 business day of receipt
Serious Adverse Events (Section 10.41)*	MedWatch Form**	At each occurrence	Within 1 business day of receipt
10.41)	Adverse Events form (see CRF packet)		Quarterly

^{*}If an adverse event meets the criteria for both an AE of Special Interest and a Serious Adverse Event, please report only as a Serious Adverse Event.

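### Three minor safety-text repairs: tumor lysis syndrome is both exempt from and subject to expedited reporting, the chemistry list omits uric acid, and AE rates exclude treated patients later found ineligible

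*Combined protocol and SAP*

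**What the plan says.** **TLS reporting.** Section 10.31 is headed "EXPECTED Serious Adverse Events: Protocol Specific Exceptions to Expedited Reporting". Its table has a column for the "CTCAE Grade at which the event will not be expeditedly reported", and TLS is listed there at Grade 3 or below. The section adds a limit: "These exceptions only apply if the adverse event does not result in hospitalization". Routine reporting still applies to exempt events. Section 10.41 lists TLS as an AESI and says "The following events are events of special interest and will require expedited reporting AT ANY GRADE". Such an event "will be treated like a serious adverse event with regard to reporting timeframes".

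**Chemistry panel.** Footnote 7 of the Test Schedule (Section 4.0) itemizes the chemistry analysis. Potassium, calcium and phosphorus are on the list; uric acid is not. Appendix III makes rasburicase mandatory for high-risk patients whose pre-dose uric acid is high. Appendix IV makes uric acid one of four analytes that define laboratory TLS.

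**AE denominator.** Endpoint 2.25 concerns regimen-related toxicity in patients treated. Section 16.325 bases AE rates on eligible patients who started treatment. Section 13.9a covers patients found ineligible after registration; if they were treated, their data must be submitted up to the point at which ineligibility is confirmed. Neither the safety summary in 16.4 nor the stopping rules in 16.522 has an eligibility filter.

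**The concern.** Section 15.17 calls TLS an important identified risk of venetoclax, particularly in CLL and MCL, so sites need one reporting instruction for it. A site that works from the 10.31 table could send a Grade 3 case without hospitalization by the routine route, while a site that works from 10.41 would expedite the same case.

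A site that orders chemistry strictly from footnote 7 would not have the uric acid value that Appendix III needs before the first venetoclax dose in a high-risk patient.

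Eligibility established after dosing does not undo exposure. Under 16.325, a treated patient later found ineligible would be left out of the AE rates but would still count in the stopping rules and in the 16.4 summary. The same trial could then report toxicity on two denominators.

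**Working it through.** **Design figures.** Section 16.24 gives 0.049 and 0.851 for the probability of declaring the regimen promising at true CR rates of 15% and 35%, and 0.790 for early stopping at 15%. The first two are the sum over x = 4 to 16 of P(Bin(16, p) = x) × P(Bin(30, p) ≥ 11 − x). This gives 0.0486 and 0.8506; P(Bin(16, 0.15) ≤ 3) = 0.7899. The design reproduces, and none of the changes below alters it.

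**(1) TLS, rule against rule.**

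| TLS case | 10.31 | 10.41 |
|---|---|---|
| Hospitalized, any grade | Exception does not apply | Expedited |
| Not hospitalized, Grade 4-5 | Above the exempt grades | Expedited |
| Not hospitalized, Grade 3 | Exempt | 24-hour notice, full report within 3 calendar days of it |
| Not hospitalized, Grade 1-2 | Exempt | Expedited as an AESI, but no site deadline |

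The rules conflict in the last two rows.

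- For Grade 3, the AESI route also has ACCRU forward the form within 1 business day. The routine route is an AE form at each evaluation, forwarded quarterly.
- For Grade 1-2, the AESI rule borrows the SAE timeframes. In the row "Not resulting in Hospitalization ≥ 24 hrs" that table requires no report for Grade 1-2. The AESI row of the reporting table asks sites to report each occurrence and sets a deadline only for ACCRU.
- Section 10.0 defines events of interest as ones not typically expedited "but that for a specific protocol are being reported via expedited means". That points to 10.41 but does not say that it overrides 10.31. A footnote in 10.41 pulls the other way: an event that "meets the criteria for both an AE of Special Interest and a Serious Adverse Event, please report only as a Serious Adverse Event". The serious-event route is the one that 10.31 exempts.
- TLS is the only term that appears by name in both lists.

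**(2) Uric acid.** Of the four Appendix IV analytes, footnote 7 lists three. Two abnormal analytes define laboratory TLS, so there are 6 minimal pairs, and 3 of them include uric acid. Appendix II orders a uric acid recheck when potassium exceeds 5.0 mmol/L, which is below the TLS threshold of 6.0. It also does so when phosphorus exceeds 4.5 mg/dL after a rise of more than 0.5. The potassium pair is therefore covered, and the phosphorus pair is covered when that rise has occurred. I give no count of uncovered cases, because Appendix II may be incomplete in the text supplied.

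**(3) AE denominator.** Inputs from 16.22: 46 evaluable patients, an allowance of 5, 6 more with de-escalation, and 63 in total if no safety-portion patient has MCL. Treated patients at full accrual are then at most N = 46 + 5 = 51, 46 + 6 + 5 = 57, or 57 + 6 = 63.

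The plan does not say how many treated patients will prove ineligible. Assume k = 0 to 5; k = 5 would use the whole allowance, which also covers cancellations and major violations. The share dropped is k/N:

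| k | N = 51 | N = 57 | N = 63 |
|---|---|---|---|
| 0 | 0% | 0% | 0% |
| 1 | 2.0% | 1.8% | 1.6% |
| 5 | 9.8% | 8.8% | 7.9% |

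If r is the rate in eligible patients and e of the k dropped patients had the event, the all-treated rate is ((N − k)r + e)/N. It differs from r by (e − kr)/N, which is at most k/N in either direction.

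Example (assumed): N = 57, k = 2, and 5 events in the 55 eligible patients. The reported rate is 5/55 = 9.1%. The all-treated rate lies between 5/57 = 8.8% and 7/57 = 12.3%.

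**The case against.** **TLS.** Appendix II says that a patient who meets its laboratory criteria within 24 hours of the first dose or an escalation should be hospitalized, and hospitalization removes the 10.31 exemption. This stands and narrows the conflict considerably. It does not remove it, because the Appendix IV window runs to 7 days after each escalation. It is also fair that 10.31 concerns expected serious events, that AESIs have their own form, and that 10.0 favors 10.41. A reader might infer that TLS as a whole could escape expedited or even routine reporting. The documents do not support that: hospitalized or Grade 4-5 TLS is expedited under both sections, and exempt events still go through routine reporting.

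**Uric acid.** The footnote's list need not be exhaustive. Appendix III implies a pre-dose value for high-risk patients, who have chemistry drawn on admission, and Appendix II rechecks uric acid after triggers. All of this stands. A reader might infer that the protocol never measures uric acid, or that half of the minimal laboratory TLS pairs would be missed. Neither follows, given those appendices.

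**AE denominator.** Few such patients are expected, because eligibility is verified at registration and waivers are barred. Their AE data are required only until ineligibility is confirmed, so adding them brings in some truncated follow-up. In the example, the shift lies well inside the exact 95% interval for 5/55, which is 3.0% to 20.0%. These points stand and keep the item small. A reader might infer that these patients' toxicities disappear from all reporting or distort stopping. Sections 16.4 and 16.522, which have no eligibility filter, show otherwise.

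**Conclusion.** The point holds as a minor one. The TLS instructions are wrong as written: two sections give opposite directions for TLS of Grade 3 or below without hospitalization, and nothing ranks them. The practical reach is mainly TLS that the Appendix II hospitalization rule does not catch.

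The other two items are cheap improvements. The uric acid item is an omission from a panel list that the appendices partly make good. The AE set departs from endpoint 2.25 by about 2% of patients for each treated ineligible patient. The upper figure of 7.9% to 9.8% requires all 5 allowance patients to be treated and later found ineligible, which is an assumption at the edge of the plan.

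None of this changes the stopping rules, the CR decision rule, power or sample size.

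**What to change.** 1. Delete the TLS row from the 10.31 table. Add to 10.41 that the Section 10.31 exceptions do not apply to AESIs. For Grade 1-2 TLS without hospitalization, state a site deadline, for example 7 calendar days, which 10.41 already uses for hospitalized Grade 1-2 events. Keep that deadline to TLS: the AESI list also includes ALT and AST increases, and a deadline for all Grade 1-2 AESIs could bring in many more forms.
2. Add uric acid to footnote 7 at the existing ramp-up draws.
3. In 16.325, define the AE set as all patients who received at least one dose of any study drug, regardless of eligibility. Note in the report that AE data for ineligible patients may stop when ineligibility is confirmed.

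The cost is protocol and SAP wording, any expedited TLS reports that would otherwise have gone by the routine route, and one analyte on blood already drawn (after rasburicase, the sample handling that Appendix III already prescribes applies). Item 3 needs no data beyond what 13.9a already collects.

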10.42 Reporting of re-occurring SAEs

ALL SERIOUS adverse events that meet the criteria outlined in Table 10.41 MUST be immediately reported to the sponsor within the timeframes detailed in the corresponding table. This reporting includes but is not limited to SAEs that re-occur again after resolution.

10.5 Other Required Reporting

- 10.51 Unanticipated Problems Involving Risks to Subjects or Others (UPIRTSOS) in general, include any incident, experience, or outcome that meets **all** of the following criteria:
 - 1. Unexpected (in terms of nature, severity, or frequency) given (a) the research procedures that are described in the protocol-related documents, such as the IRB-approved research protocol and informed consent document; and (b) the characteristics of the subject population being studied;
 - 2. Related or possibly related to participation in the research (in this guidance document, possibly related means there is a reasonable possibility that the incident, experience, or outcome may have been caused by the procedures

^{**} MedWatch form can be found on the ACCRU website.

- involved in the research); and
- 3. Suggests that the research places subjects or others at a greater risk of harm (including physical, psychological, economic, or social harm) than was previously known or recognized.

Some unanticipated problems involve social or economic harm instead of the physical or psychological harm associated with adverse events. In other cases, unanticipated problems place subjects or others at increased *risk* of harm, but no harm occurs.

If the event meets the criteria for an UPIRTSO, submit to your IRB as required by your institutional policies.

10.52 Baseline and Adverse Events Evaluations

The following pre-treatment symptoms/conditions are to be graded at baseline and at each evaluation using CTCAE v5.0 grading.

System Organ Class (SOC)	Adverse Event/Symptoms	Baseline	Each evaluation
Nervous system disorders	Peripheral Sensory Neuropathy	X	X
Blood and lymphatic system disorders	Anemia	X	X
Investigations	Neutrophil count decreased	X	X

10.53 Case Report Forms - Academic and Community Cancer Research United (ACCRU)

Submit the following AEs not specified in Section 10.5. Submit via appropriate Academic and Community Cancer Research United (ACCRU) Case Report Forms (i.e., paper or electronic, as applicable) the following AEs experienced by a patient and not specified in Section 10.5:

- 10.531 Grade 2 AEs deemed *possibly, probably, or definitely* related to the study treatment or procedure.
- 10.532 Grade 3 and 4 AEs regardless of attribution to the study treatment or procedure

10.533 Grade 5 AEs (Deaths)

- -Any death $\underline{\text{within 30 days}}$ of the patient's last study treatment or procedure regardless of attribution to the study treatment or procedure requires expedited reporting within 24-hours .
- -Any death more than 30 days after the patient's last study treatment or procedure that is felt to be at least possibly treatment related must also be submitted as a Grade 5 AE, with a CTCAE type and attribution assigned.
- 10.54 Late occurring adverse events are any adverse events that occur during Clinical

- Follow-Up and Survival Follow-Up reporting periods. These are reported in compliance with Section 4.0 and Section 18.0.
- 10.55 Reconciliation: ACCRU agrees to conduct reconciliation for the product. Genentech and ACCRU will agree to the reconciliation periodicity and format but agree at maximum to exchange quarterly line listings of cases received by the other party. If discrepancies are identified, the Sponsor and Genentech will cooperate in resolving the discrepancies. The responsible individuals for each party shall handle the matter on a case-by-case basis until satisfactory resolution.
- 10.56 Quarterly Report: ACCRU will provide Genentech with accrual and a toxicity report on a quarterly basis.
- 10.57 IND Annual Reports: All IND annual reports submitted to the FDA by the Sponsor-Investigator should be copied to Genentech.

11.0 Treatment Evaluation

Lugano Classification Response Criteria

11.1 Response Considerations

Schedule of Evaluations: PET/CT scans are required at baseline for all patients. For the purposes of this study, patients should be reevaluated for disease progression at the end of induction therapy and every 6 months during maintenance or per standard of care. Definitions for clinical response for patients with lymphoma are from the recently revised Cheson's et al criteria published in 2014, derived from the original criteria published in 2007. (Cheson et al, 2014) (Cheson et al, 2007). Lymph node measurements should be taken from the CT portion of the PET/CT, or other dedicated CT scans where applicable. Measurement of lymphadenopathy for purposes of assessing for PR will be determined by adding the sum of the products of the maximal perpendicular diameters of measured lesions (SPD). The PPD of a single node is sufficient to evaluate for PD (see Table 11.2). Measurable extranodal disease should be assessed in a manner similar to that for nodal disease. For these recommendations, the spleen is considered nodal disease. Disease that is only assessable (eg, pleural effusions, bone lesions) will be recorded as present or absent only, unless, while an abnormality is still noted by imaging studies or physical examination, it is found to be histologically and pathologically negative.

Response is based on PET/CT based on the revised 2014 Lugano Classification. (Cheson et al, 2014).

Progressive disease is based on either PET-CT based or CT based response criteria. PET confirmation of progressive disease is per physician discretion.

11.2 Lugano Classification Response criteria (Cheson et al, 2014)

	PET-CT Based Response	CT-Based Response
Complete	Complete metabolic response (CR)	Complete radiologic response (CR)
Response		(all of the following)

Lymph nodes and extralymphatic sites	Score 1, 2, or 3* with or without a residual mass on 5PS† It is recognized that in Waldeyer's ring or extranodal sites with high physiologic uptake or with activation within spleen or marrow (eg, with chemotherapy or myeloid colony-stimulating factors), uptake may be greater than normal mediastinum and/or liver. In this circumstance, complete metabolic response may be inferred if uptake at sites of initial involvement is no greater than surrounding normal tissue even if the tissue has high physiologic uptake	Target nodes/nodal masses must regress to ≤ 1.5 cm in LDi No extralymphatic sites of disease
Nonmeasured lesion	Not applicable	Absent
Organ enlargement	Not applicable	Regress to normal
New lesions	None	None
Bone marrow	No evidence of FDG-avid disease in	Normal by morphology; if
	marrow	indeterminate, IHC negative
Partial Response	Partial metabolic response (PR)	Partial remission (PR) (all of the following)
Lymph nodes and extralymphatic sites	Score 4 or 5† with reduced uptake compared with baseline and residual mass(es) of any size At interim, these findings suggest responding disease At end of treatment, these findings indicate residual disease	≥ 50% decrease in SPD of up to 6 target measurable nodes and extranodal sites When a lesion is too small to measure on CT, assign 5 mm X 5 mm as the default value When no longer visible, 0 X 0 mm For a node > 5 mm X 5 mm, but smaller than normal, use actual measurement for calculation
Nonmeasured lesions	Not applicable	Absent/normal, regressed, but no increase
Organ enlargement	Not applicable	Spleen must have regressed by > 50% in length beyond normal
New lesions	None	None
Bone marrow	Residual uptake higher than uptake in normal marrow but reduced compared with baseline (diffuse uptake compatible with reactive changes from chemotherapy allowed). If there are persistent focal changes in the marrow in the context of a nodal response, consideration should be given to further evaluation with MRI or biopsy or an interval scan	Not Applicable

No Response	No metabolic response (SD)	Stable disease (SD)
or Stable	1 ()	~~~~~~~~~~~~~~~~~~~~~~~~~~~~~~~~~~~~~~~
Disease		
Target nodes/nodal masses, extranodal lesions	Score 4 or 5 with no significant change in FDG uptake from baseline at interim or end of treatment	< 50% decrease from baseline in SPD of up to 6 dominant, measurable nodes and extranodal sites; no criteria for progressive disease are met
Nonmeasured	Not applicable	No increase consistent with progression
lesions	11	1 5
Organ enlargement	Not applicable	No increase consistent with progression
New lesions	None	None
Bone marrow	No change from baseline	Not Applicable
Progressive	Progressive metabolic disease (PD)	Progressive disease (PD)
disease		requires at least 1 of the following
Individual target nodes/nodal masses Extranodal lesions	Score 4 or 5 with an increase in intensity of uptake from baseline and/or New FDG-avid foci consistent with lymphoma at interim or end-of-treatment assessment	PPD progression: An individual node/lesion must be abnormal with: $LDi > 1.5 \text{ cm and}$ $Increase by \geq 50\% \text{ from PPD nadir and}$ An increase in LDi or SDi from nadir 0.5 cm for lesions ≤ 2 cm 1.0 cm for lesions ≥ 2 cm In the setting of splenomegaly, the splenic length must increase by $\geq 50\%$ of the extent of its prior increase beyond baseline (eg, a 15-cm spleen must increase to ≥ 16 cm). If no prior splenomegaly, must increase by at least 2 cm from baseline New or recurrent splenomegaly
Nonmeasured lesions	None	New or clear progression of preexisting nonmeasured lesions
New lesions	New FDG-avid foci consistent with lymphoma rather than another etiology (eg, infection, inflammation). If uncertain regarding etiology of new lesions, biopsy or interval scan may be considered	Regrowth of previously resolved lesions A new node > 1.5 cm in any axis A new extranodal site > 1.0 cm in any axis; if < 1.0 cm in any axis, its presence must be unequivocal and must be attributable to lymphoma Assessable disease of any size unequivocally attributable to lymphoma
Bone marrow	New or recurrent FDG-avid foci	New or recurrent involvement

Abbreviations: 5PS, 5-point scale; CT, computed tomography; FDG, fluorodeoxyglucose; IHC, immunohistochemistry; LDi, longest transverse diameter of a lesion; MRI, magnetic resonance imaging; PET, positron emission tomography; PPD, cross product of the LDi and perpendicular diameter; SDi, shortest axis perpendicular to the LDi; SPD, sum of the product of the perpendicular diameters for multiple lesions.

*A score of 3 in many patients indicates a good prognosis with standard treatment, especially if at the time

of an interim scan. However, in trials involving PET where de-escalation is investigated, it may be preferable to consider a score of 3 as inadequate response (to avoid under treatment). Measured dominant lesions: Up to six of the largest dominant nodes, nodal masses, and extranodal lesions selected to be clearly measurable in two diameters. Nodes should preferably be from disparate regions of the body and should include, where applicable, mediastinal and retroperitoneal areas. Non- nodal lesions include those in solid organs (eg, liver, spleen, kidneys, lungs), GI involvement, cutaneous lesions, or those noted on palpation. Nonmeasured lesions: Any disease not selected as measured, dominant disease and truly assessable disease should be considered not measured. These sites include any nodes, nodal masses, and extranodal sites not selected as dominant or measurable or

that do not meet the requirements for measurability but are still considered abnormal, as well as truly assessable disease, which is any site of suspected disease that would be difficult to follow quantitatively with measurement, including pleural effusions, ascites, bone lesions, leptomeningeal disease, abdominal masses, and other lesions that cannot be confirmed and followed by imaging. In Waldeyer's ring or in extranodal sites (eg, GI tract, liver, bone marrow), FDG uptake may be greater than in the mediastinum with complete metabolic response but should be no higher than surrounding normal physiologic uptake (eg, with marrow activation as a result of chemotherapy or myeloid growth factors).

†PET Deauville 5PS: 1, no uptake above background; 2, uptake≤mediastinum; 3, uptake > mediastinum but ≤ liver; 4, uptake moderately > liver; 5, uptake markedly higher than liver and/or new lesions; X, new areas of uptake unlikely to be related to lymphoma.

